4.4.13. Visit 12: Day 35 – End of intervention

Visiting window: +/- 2 days compared to day 0. CT- and DXA-scans to be performed +/- 3 days from visit 12 on day 35.

Subjects will be entitled to another visit with an investigator and a study nurse 5 weeks after the start of intervention. The subject is required to have had an overnight fast before this visit and not have eaten anything before the study visit, this due to the blood sampling. Study subjects will have worn the vests for 8 hours the day before, but they will not wear it during the visit the morning of day 35.

The research subject will be questioned regarding possible adverse events.

The following examinations will be performed:

- Physical examination
- Blood pressure
- Body weight
- Fat mass, water mass and fat free mass will be measured using BIA
- Waist circumference
- Fasting venous blood sampling
- Fasting capillary blood sample for measurement of glucose level

Close to this visit (+/- 3 days) participants will go through a CT- and DXA-scan. Procedures will be performed by experienced personnel operating the CT- and DXA-scan.

The day before visit 13 subjects will receive a text message to their mobile phone with a reminder regarding the fasting blood samples on visit 13.

4.4.14. Visit 13: Day 49 - Follow up visit

Visiting window: +/- 3 days.

Study code:
Clinical Study Protocol

Version No:
Detail

Version No: 14.9
Date: 2021-02-01

ATLAS

Subjects are invited to a follow up visit at the study center 2 weeks after the end of intervention. The subject is required to have had an overnight fast before this visit and not have eaten anything before the study visit, this due to the blood sampling.

During the meeting on study day 49 the following examinations will be performed:

- Physical examination
- Blood pressure
- Body weight
- Fat mass, water mass and fat free mass will be measured using BIA
- Waist circumference
- Fasting venous blood sampling
- Fasting capillary blood sample for measurement of glucose level

At this meeting the subject will also be questioned regarding regression of possible adverse events.

4.5. Biological sampling procedures

4.5.1. Handling, storage and destruction of biological samples

To determine the mechanism of action and elucidate the beneficial effects of body weight loading we will analyze blood samples. Some tubes may be used for analyzes by Sahlgrenska University Hospital local lab and the rest of the tubes will be used for analyzes by the research group at the Institute of Neurophysiology and Physiology, Sahlgrenska Academy, University of Gothenburg. All samples will be pseudonymized and labeled according to a separate log. Measurements will be performed as quickly as possible and samples will then be destroyed. At any time, a study subject can request destruction of his or her blood samples.

Each venous blood drawing consists of approximately 35 ml divided into approximately between 4-10 tubes. The tubes used for blood drawings may contain ethylenediaminetetraacetic acid (EDTA) or a SST-gel for the purpose of manipulating coagulation.

Analysis performed by local lab at Sahlgrenska University Hospital: serum concentration of Hemoglobin (Hb), White Blood Cell Count (WBC), thrombocyte count, sodium (Na), potassium (K), chloride (CI), calcium (Ca), creatinine, aspartate transaminase (AST), alanine transaminase (ALT), alkaline phosphatase (ALP), total bilirubin, Prothrombin Time (PT-INR), Activated Partial Thromboplastin Time (APTT), human immunodeficiency viruses (HIV), Hepatitis B, Hepatitis C, glycated hemoglobin (HbA1c), C-reactive protein (CRP), free thyroxine (fT4), thyroid stimulating hormone (TSH), insulin, High-density lipoprotein (HDL), Low-density lipoprotein (LDL) and triglycerides.

Fasting blood glucose levels will be measured directly at the study center in capillary blood by using Hemocue[®] glucose system.

Analysis performed at the Sahlgrenska Academy, University of Gothenburg: Fibroblast Growth Factor 21 (FGF21), FGF23, FGF15, osteocalcin, sclerostin, lipocalin2, leptin, ghrelin, Glucagon-like peptide-1 (GLP-1), GLP-2, CCK, (3-36) PYY, glucagon, testosterone, estrogens, renin, glycerol, free fatty acids (FFA) and methoxynorepinephrine.

Exploratory analysis in serum of circulating proteins, metabolites or electrolytes may be performed. Serum analysis in form of proteomics or metabolomics may also be executed.

Study code: ATLAS
Clinical Study Protocol Version No: 14.9
Poto: 2021 0:

Date: 2021-02-01

Urine samples from the doubly labeled water measurements will be sent to a cooperative research group at Maastricht University in the Netherlands for analysis. All samples will be pseudonymized during the full process and labeled according to a separate log. All samples will be returned to Sahlgrenska University Hospital or destroyed after analysis. Handling and shipment of samples will follow all applying regulations.

All samples will be stored and handled according to the biobank agreement with Biobank Väst (reg. number 890). This has been reported to the Swedish "Health and Social Care Inspectorate" according to regulation 2002:297.

If we experience technical difficulties measuring any of the above mentioned parameters some samples may be sent to another EU/EES country or to other countries internationally for measurements. The samples will then be pseudonymized during the full process. The analysis may take place at a cooperative research group, the industry or drug manufacturer. The samples will be returned or destroyed upon completed analysis. Sending and handling of samples will be according to all applied laws and regulations.

4.5.2. Total volume of blood per subject

Each blood sample will consist of approximately 35 ml blood divided into 4-10 tubes. The total volume of blood taken from each subject during the study is approximately 175 ml. In comparison, a blood donation consists of up to 450 ml.

4.5.3. Total volume of urine per subject

Subjects will collect a total of 14 urine samples divided equally over two doubly labeled water measurements. For each sample the whole voiding will be collected in a plastic container with a total volume of 500-1000 ml. A total of 14 containers will be collected from each subject and the urine volume in each container will depend on the individual voiding volume. At the study center 2 ml of urine will be transferred from each plastic container into two separate glass vials. One of these vials with 2 ml urine will then be sent to Maastricht University, The Netherlands, for analysis. The other vial will be stored according to the biobank agreement. Thus, a total of 56 ml urine will be collected from each subject for analysis. The remaining urine in the plastic containers will be destroyed.

4.5.4. Biobank

All biological samples taken in this study are registered in a biobank according to an agreement with Biobank Väst (registration nr: 890) and handled according to the current biobank laws and regulations (Biobankslagen SFS 2002:297) concerning biobanks in health service and care. The law regulates the way samples can be stored and used as well as regulation about quality and safety for biobanks. The samples will be stored prior to analysis and coded/pseudonymized to protect the identification of the subjects. All samples and the identification/code list are stored securely and separately to prevent unauthorized persons from having access to them. Eventual sending of samples will be done according to current laws and regulations and applied material transfer agreements.

4.6. End of study

The study ends when the last subject has completed the last follow-up, defined as the last visit of the last subject (LVLS). The study may be prematurely terminated if it appears that the treatment involved many serious adverse events (SAE) or if recruitment of subjects cannot be met within

Study code: ATLAS
Version No: 14.9
Date: 2021-02-01

reasonable time limits. If the study is prematurely terminated or suspended, the investigator should immediately inform the subjects about this and ensure appropriate treatment and follow-up. The regulatory authority should be informed as soon as possible, but no later than within 15 days, by the PI, investigator or sponsor.

Decisions on premature termination are taken by the sponsor.

The sponsor, PI or investigator will notify the concerned Ethics Committee and the Competent Authorities at the end of the study within a period of 90 days.

5. STUDY POPULATION

5.1. Inclusion criteria

For inclusion in the study, subjects must fulfil all of the following criteria:

- 1. Signed informed consent to participate in the study.
- 2. Consent out of free will.
- 3. 18-65 years of age.
- 4. Obesity as defined by a BMI >30 and ≤35. Fat mass above 25 % [2].
- 5. Willingness to comply with the study protocol.
- 6. Normal or clinically non-significant screening of blood samples:
 - a. Hemoglobin (Hb), White Blood Cell Count (WBC), thrombocyte count, sodium (Na), potassium (K), chloride (Cl), calcium (Ca), creatinine, aspartate transaminase (AST), alanine transaminase (ALT), alkaline phosphatase (ALP), total bilirubin, Prothrombin Time (PT-INR), Activated Partial Thromboplastin Time (APTT), human immunodeficiency viruses (HIV), Hepatitis B, Hepatitis C, glycated hemoglobin (HbA1c), C-reactive protein (CRP), free thyroxine (fT4), thyroid stimulating hormone (TSH).
 - b. Normal or clinically non-significant aberrations of screening blood samples are defined as:
 - i. Normal: Values within the reference interval supplied by the local lab at Sahlgrenska University Hospital
 - ii. Clinically non-significant aberration: as judged by investigator (Clinical significance judged by investigator)
- 7. Normal or non-clinically significant 12-lead electrocardiography (ECG) recording as judged by the investigator.

5.2. Exclusion criteria

Subjects must not be included in the study if any of the following criteria are fulfilled:

 Chronic disease that could interfere with the participation in the study as judged by the investigator. For example poorly regulated type 1 or type 2 diabetes, cardiovascular disease that effect daily life, pulmonary disease that affects daily life, anemia or malignancy. Study code: ATLAS
Clinical Study Protocol Version No: 14.9
Date: 2021-02-01

2. Chronic pain such as pain that is constant and impairs quality of life as judged by the investigator; for example: significant back, hip and knee pain.

- 3. Regular consumption of medicine or natural supplements that affect weight, inhibit physical activity or increase the risk of adverse effects as judged by the investigator. The following drugs will not be accepted:
 - a. β-blockers, GLP-1-agonists, DPP-IV-inhibitors, SGLT2-inhibitors, sulfonylureas, insulin, orlistat, anti-obesity drugs, antidepressants, bisphosphonates, β2-agonists, oral corticosteroids, diuretics, benzodiazepines, or central nervous system stimulating drugs such as methylphenidate or dextroamphetamine.
 - b. Any illegal drugs according to local laws and regulation
- 4. Gastric by-pass surgery or equivalent metabolic surgery in the gastrointestinal tract.
- 5. Reduced mobility.
- 6. Pregnancy. Females of childbearing potential must confirm to use reliable contraception (intrauterine device, oral contraceptives or condom) and not suspect to be pregnant. Pregnancy test will be taken on all female subjects of fertile age unless permanently sterile, as judged by the investigator. Permanently sterile women can be excluded from the pregnancy test. Permanent sterilization methods include hysterectomy, bilateral salpingectomy and bilateral oophorectomy.
- 7. Change in body weight of 5 kg or greater during the past 3 months or recently started a strict diet. Also, a greater change in body weight than 3 kg difference between day -21 and day 0 will not be accepted.
- 8. Use of any illegal drugs according to local regulations or consuming excessive amounts of alcohol, tobacco, nicotine.
 - a. Excessive amounts of above-mentioned substances defined as:
 - Consumption of more than 9 glasses of wine for women, 14 glasses of wine for men (15 cl/glass 11 % alcohol) or equivalent as judged by the investigator during an ordinary week will not be accepted.
 - ii. Individuals with a consumption equal or higher than 10 cigarettes or half a packet of snuff per day.
- 9. Drastic change in lifestyle during the last 3 months; for example a significant change in physical activity, dietary habits, nicotine, alcohol or drug use as judged by the investigator.
- 10. Apparent risk of not being able to comply with the study protocol for any reason as judged by the investigator.
- 11. Having participated in a similar study during the last 6 months.

Reasons for exclusion of participants will be reported in the publication.

5.3. Restrictions

The study subjects will be required to wear the weight vests for 8 hours per day. It is allowed to wear the vest in intervals as long as a total wearing time of 8 hours per day is achieved. Subjects who deviate more than 20 % from this (i.e. use the vest for less than 6.4 hours during the daily 8-

Study code: ATLAS
Version No: 14.9

Date: 2021-02-01

hour vest wearing period) will be excluded from the study. Deviation from vest wearing time will be calculated as a mean of the total vest wearing time for all 5 intervention weeks, this at the end of the intervention (day 35).

The study subjects are required to be in a standing position a minimum of 2 hours per day while wearing the weight vest. Subjects who deviate more than 20 % from this (i.e. standing less than 96 minutes during the daily 8-hour vest wearing period) will be excluded from the study. Deviation from standing time will be calculated as a mean of the total standing time for all 5 intervention weeks, this at the end of the intervention (day 35). Subjects will also be encouraged to be in a standing position as many hours possible of the vest wearing time.

The study subjects are only allowed to consume a limited amount of alcohol and other drugs during the study. This in line with the inclusion- and exclusion criteria.

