INVESTIGATOR	[name]	Sahlgrensk a University Hospital, Molecular and Clinical Medicine	[name]	[name]	Per- [contact]
INVESTIGATOR	[name]	University of Gothenburg , Department of Physiology	[name]	[contact]	john- [contact]
INVESTIGATOR	[name]	University of Gothenburg , Department of Physiology	[name]	[name]	[contact]
MONITOR	[name]	Gothia Forum	[name]	[name]	[contact]
STUDY NURSE	[name]	Clinical Trial Center, Sahlgrensk a University Hospital	[name]	[name]	[contact]

Study code: ATLAS
Version No: 14.9

Date: 2021-02-01

LIST OF USED ACRONYMS AND ABBREVIATIONS

Abbreviation	Term/Explanation
AE	Adverse Event = any untoward medical occurrence
ANOVA	Analysis of Variance
AR	Adverse Reaction = adverse event, that is each unfavorable and unexpected reaction to a study treatment, regardless of dose
В	Blood
BIA	Bioelectrical Impedance Analysis
BMI	Body Mass Index
CT	Computed Tomography
DSUR	Development Safety Update Report = annual safety report
DXA	Dual energy X-ray Absorptiometry
eCRF	Electronic Case Report Form
EPM	Etikprövningsmyndigheten (English: Swedish Ethical Review Authority)
GCP	Good Clinical Practice
HRV	Heart Rate Variability
HU	Hounsfield Units
ICH	International Council for Harmonization
ITT	Intention-to-treat = including data from all subjects who have been
111	randomized and wore a weight vest at least 2.5 weeks
LVFS	Läkemedelsverkets författningssamling (English: Swedish Medical Products Agency's statutes)
Р	Plasma
PCR	Polymerase Chain Reaction
PI	Principal Investigator
	Per Protocol analysis = including only data from subjects who have
PP	completed the study completely in accordance with the protocol, with no
	deviations from the protocol
S	Serum
SAE	Serious Adverse Event = serious untoward medical occurrence
SDQ	Short Dietary Questionnaire
SPC or SmPC	Summary of Product Characteristics
SUSAR	Suspected Unexpected Serious Adverse Reaction
BFR	Bild och Funktionsregistret (imaging storage database)

Study code: **ATLAS** Clinical Study Protocol Version No: 14.9

2021-02-01 Date:

LIST OF APPENDICES

- 17.1. Short Dietary Questionnaire (SDQ)
- 17.2. Physical Activity Diary

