5.4. Subject enrolment and randomization

Healthy subjects will be recruited by advertising in a local newspaper, on social media, on websites, on bulletin boards or with flyers. Only healthy subjects will be enrolled. Each study subject will be given an enrollment number (E-number) at screening. Subjects eligible for randomization will be randomized either to wear heavy weight vest (intervention/high load group) or to wear a light weight vest (control/low load group). Subjects will at randomization receive a randomization number linked to the enrollment number. We will aim to recruit participants until 25 participants in the heavy weight vest group and 25 participants in the light weight vest group have completed the study, i.e. performed visits at day 0 and day 35 and are eligible for analysis of the primary endpoint. In the end, this gives a total of 50 participants who will complete the study according to full analysis set for analysis of the primary endpoint.

Only the study nurse, investigator and the PI will be able to connect each study subject with their enrolment number or randomization number. Identification of individual study subjects will only be performed under special circumstances, for example, if a study subject requests removal of his or her study data.

Study subject eligibility will be established before enrolment and randomization; to be included in the study, the study subject must meet all inclusion and no exclusion criteria. Study subjects will be randomized as study subjects are eligible for randomization. If a study subject discontinues from the study, the study enrolment number or randomization number will not be reused, and the study subject will not be allowed to re-enter the study.

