9. STATISTICS

9.1. Analysis population

The aim of this trial is to further elucidate the effect increased artificial loading has on body weight. It is important to identify if there is any effect of increased loading on obese subjects under optimal conditions and if all subjects are fully compliant to the study protocol. Therefore all participants that complete the study with regards to the primary outcome will be included in the analysis, e.g. analyses applicable to Full Analysis Set (FAS). A secondary per protocol analysis may be performed with regards to the study endpoints.

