9.2.2. Drop-outs

Subjects who have not completed study visit on day 0 (start of intervention) and on day 35 (end of intervention) will be excluded from the analysis due to not being eligible for analysis of the primary endpoint.

Subjects who have used the weight vest less than 80% of requested time will be excluded from a possible additional per protocol analysis but not from the primary FAS analysis. Wearing time will be calculated as a mean of the total wearing time for the 5 weeks of intervention. Wearing time of 8 hours per day gives a total wearing time of 280 hours and subjects are thus required to wear the vest for at least 224 hours during the intervention period. This will be calculated after the end of intervention (day 35) based on self-reporting

Subjects who have been in a standing position (while wearing the weight vest) less than 80% of requested time will be excluded from a possible additional per protocol analysis but not from the primary FAS analysis. Standing time will be calculated as a mean of the total standing time for the 5 weeks of intervention. Standing time of 2 hours per day gives a total wearing time of 70 hours and subjects are thus required to be in a standing position for at least 56 hours during the intervention period. This will be calculated after the end of intervention (day 35) based on self-reporting

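### Section 5.3 removes participants below 80% of wearing or standing time from the study, while section 9.2.2 keeps the same participants in the primary analysis

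*Protocol*

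**What the plan says.** **Section 5.3 (Restrictions).** A participant more than 20% short of the 8 h daily wearing time is removed: "hour vest wearing period) will be excluded from the study. Deviation from vest wearing time will be calculated as a mean". The mean is taken over all five intervention weeks, at day 35. The standing rule is built the same way: "i.e. standing less than 96 minutes during the daily 8-hour vest wearing period) will be excluded from the study".

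**Section 9.2.2 (Drop-outs).** For wearing time: "Subjects who have used the weight vest less than 80% of requested time will be excluded from a possible additional per protocol analysis". For standing time too, those short of the limit are "excluded from a possible additional per protocol analysis but not from the primary FAS analysis".

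**Other sections that define the primary set.** Section 9.1 states that "all participants that complete the study with regards to the primary outcome will be included in the analysis". Section 5.4 counts towards the target those who have "performed visits at day 0 and day 35 and are eligible for analysis of the primary endpoint". Section 9.3 defines eligibility for the full analysis set (FAS) by the same two visits. None of the three has a wearing or standing criterion.

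**Section 5.5 (Withdrawal criteria).** Whether a non-compliant participant continues is left to the investigator.

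**List of acronyms and abbreviations.** ITT covers those "randomized and wore a weight vest at least 2.5 weeks". The per-protocol entry allows no protocol deviations at all.

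**The concern.** The two sections use one measure, at one time point, with one cut-off, and attach opposite consequences to it. Section 5.3 is not easily read as a rule for stopping the intervention, because the deviation is calculated only at day 35. By then the vest period is over and the primary weight is due (section 4.4.13). Removal at that point can only mean losing the participant's data, the day 49 follow-up, or both.

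If it means losing the data, the randomized comparison becomes one selected on adherence. That adherence is self-reported in the vest diary (sections 7.1.2.11 and 9.2.2). Participants know the hypothesis that a vest may lower body weight (section 4.1). The protocol also gives a reason why adherence might differ by arm: section 2.3 reports more musculoskeletal complaints under high load in the earlier three-week study and considers increased axial loading the probable cause. Exclusion that differs between an 11% and a 1% vest would undo the balance that randomization provides, and a larger sample would not repair it. The loss of numbers, and so of power, comes on top.

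**Working it through.** **1. Are the thresholds the same?**

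| Quantity | Section 5.3 (per day) | Over 35 days | Section 9.2.2 (total) |
|---|---|---|---|
| Wearing | 0.8 × 8 h = 6.4 h | 6.4 × 35 = 224 h | 0.8 × 280 h = 224 h |
| Standing | 0.8 × 120 min = 96 min | 96 × 35 = 3,360 min = 56 h | 0.8 × 70 h = 56 h |

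They are identical, so both sections concern exactly the same participants.

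**2. Reproducing the planned sample size.** Inputs from section 9.3: difference 1.6 percentage points, SD 2, p<0.05 (taken as two-sided), power 80%. Allocation is 1:1 (section 6.1).

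- n per group = 2 × (1.960 + 0.842)² × 2² / 1.6² = 24.5, rounded up to 25. This matches the plan.
- Power at 25 per group = Φ(1.6 / (2 × √(2/25)) − 1.960) = Φ(2.828 − 1.960) = Φ(0.868) = 80.7%.
- With the t distribution the requirement is 26 per group, and power at 25 is 79.1%. The difference is immaterial here.

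The 25 per group is tied in section 9.3 to completers of the day 0 and day 35 visits. It therefore fits the rule in 9.2.2 and makes no allowance for removals under 5.3.

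**3. If 5.3 removed completers.** The documents give no non-adherence rate, so the rates below are assumptions. They are applied equally to both arms, with difference and SD unchanged. With m = 25 × (1 − rate) per group, power = Φ(0.8 × √(m/2) − 1.960). Keeping 25 per group instead would mean screening 125/(1 − rate), where 125 = 50/0.8/0.5 from the plan's 20% dropout and 50% screening failure. The plan states approximately 130.

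| Removed | Total left of 50 | Power without replacement | Screened if replaced |
|---|---|---|---|
| 0% | 50 | 80.7% | 125 |
| 5% | 47.5 | 78.7% | 132 |
| 10% | 45 | 76.5% | 139 |
| 20% | 40 | 71.6% | 157 |
| 30% | 35 | 65.8% | 179 |

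This table shows loss of numbers only. Bias from unequal removal between arms cannot be sized from the documents.

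**The case against.** The strongest reply is that the protocol already settles the analysis question. Sections 5.4, 9.1, 9.2.2 and 9.3 all define the primary set by the two visits. Section 9.2.2 addresses this very case and keeps the participants in. Section 5.3 is a conduct section and names no analysis set, so an analyst would have to depart from section 9 to act on it. That stands, and it limits the point to a conflict between one conduct section and a consistent statistics section. It does not make 5.3 harmless: its wording is mandatory, and site staff could follow it before any analyst sees the data. Section 9.1 also justifies its choice by an interest in the effect under full compliance, which sits more easily with 5.3 than with a set that retains poor adherers.

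A reader might infer more than the documents support:

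- *That the primary population is undefined, or open to choice once results are known.* Section 9 names it in advance.
- *That the 2.5-week ITT entry is a third competing rule.* The term is defined only in the abbreviation list and is never linked to the primary endpoint. The per-protocol mismatch concerns an analysis that is only optional.
- *That 5.3 decides who counts towards 25 per arm.* Section 5.3 does not mention the target, and 5.4 and 9.3 count by visits.
- *That a particular imbalance between arms can be predicted.* There are no adherence data. In the earlier study, discontinuations for musculoskeletal events were equal, at one per arm (section 2.3).
- *That the trial is declared open-label.* The protocol does not state its blinding status. That participants could tell an 11% vest from a 1% vest is an inference.

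**Conclusion.** The contradiction is real and lies in the current text. Sections 5.3 and 9.2.2 give opposite consequences for the same participants, and 5.3 is the section out of line with the rest of the protocol. Applied to the data, it would mean post-randomization exclusion on self-reported adherence.

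The size is conditional. If section 9 is followed, nothing is lost. If 5.3 is followed without replacement, power falls from about 81% to between 79% (5% removed) and 66% (30% removed). Those figures assume equal removal in both arms, the planned difference and SD, and the normal approximation. The possible bias from unequal removal is the more serious consequence and cannot be quantified here. The entries in the abbreviation list are minor.

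**What to change.** - In both 5.3 sentences (wearing and standing), replace removal from the study with wording to this effect: participants below the limit are left out of the possible per-protocol analysis only, as in 9.2.2; their day 0 and day 35 data remain in the primary FAS and count towards the 25 per group.
- Reconcile 5.3 with section 5.5, which leaves continuation after non-compliance to the investigator. This point concerns use of the data and does not prescribe the withdrawal rule.
- As tidying, delete the unused 2.5-week ITT definition and align the per-protocol entry in the abbreviation list with the 80% limits in 9.2.2.

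The cost is a few wording changes, with no new data and no change to the sample size. The drawback is that keeping poor adherers may dilute the estimate, which section 9 already accepts. As an outer bound, suppose 10% of the high-load arm were below the limit and had no effect at all. The expected difference would then be 1.6 × 0.9 = 1.44 points and power about 72%. Participants just short of 80% would dilute far less. The case for the change is therefore comparability of the arms rather than gain in power.
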